8.8 Prior and concomitant therapy

Any prior or concomitant therapy that the patient may be taking and may be necessary for the patient's welfare taken within two weeks prior to the start of the study and during the study must be recorded in the patient's source documentation and in the CRF (including start/stop dates, dose frequency, route of administration, and indication).

The patient may be on a stable, continuous regimen of fiber, or probiotics one month before the Screening Visit; however, he/she must maintain a stable dose regimen through Week 12. Additionally, certain drugs used for the treatment of IBS (e.g. low dose tricyclic antidepressants) may be allowed at the discretion of the Medical Monitor provided the patient remains on a stable dose for one month prior to the Screening Visit and throughout the study with the exception of tegaserod, lubiprostone, linaclotide, metoclopramide, prucalopride, domperidone, plecanatide, CandiBactin, Atrantil, Allimax/Allimed within 2 weeks prior to the Screening Visit or antibiotics within 2 months prior to the Screening Visit.

Rescue medication will be allowed for severe constipation (i.e. when symptoms become intolerable). For guidance purposes for this protocol, intolerable symptoms may be when a subject has not had a complete spontaneous bowel movement (CSBM) in the preceding three days with an abdominal pain score of \geq 6 on an 11-point (0-10) scale each day during that time period. However, intolerability is ultimately a subjective judgment, and principal investigators and their patients make the final decision regarding what is intolerable and requires use of the rescue medication. For the Randomization Visit only, rescue medication will not be allowed the day before, the day of, or the calendar day after the Randomization Visit. If rescue medication is taken during this time, it must be recorded as a protocol deviation and the subject should not be randomized. The use of protocol-specified rescue medication and non-protocol-specified laxatives will be recorded in the subject record.

Permitted rescue medications include bisacodyl, magnesium citrate, magnesium hydroxide, and lactulose. Dosage and frequency should be followed according to package insert on rescue medication and should not exceed recommended doses as approved by package insert.

9. Procedures and variables

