13.3 Daily questionnaire

Did you have a bowel movement today?

If yes, did it feel complete?

What did it look like? Please use the Bristol Stool Chart as a reference.

Did you have more than one bowel movement today?

If yes, did it feel complete?

What did it look like?

Did you have more than two bowel movements today?

If yes, did it feel complete?

What did it look like?

Did you take a laxative today?

Date: June 30. 2020	Version: 8.0	Page: 46 of 52

If yes, please specify: Protocol-recommended rescue medication (bisacodyl, magnesium citrate, magnesium hydroxide, or lactulose) or Other laxative (oral, suppository, or enema)

If other, please specify the name of the laxative taken.

How severe has straining been during your bowel movements over the last 24 hours.

- 0 None (absent)
- 1 Mild (not very severe)
- 2 Moderate (somewhat severe)
- 3 Severe
- 4 Very Severe

Using the scale above, please rate the worst level of abdominal pain you have felt over the past 24 hours.

Bloating is a condition in which the belly (abdomen) feels full and tight or may look or feel swollen/distended. Patients may experience abdominal fullness, pressure, or a sensation of trapped gas.

Please rate the worst level of bloating you have felt over the last 24 hours.

- 0 None (absent)
- 1 Mild (not very severe)
- 2 Moderate (somewhat severe)
- 3 Severe
- 4 Very Severe

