#### 3. ENDPOINTS

#### 3.1. PRIMARY EFFICACY ENDPOINT

The primary efficacy endpoint is the change from baseline in the weekly average number of complete spontaneous bowel movements [CSBMs] during the 12-week Treatment Period.

A CSBM is a spontaneous bowel movement [SBM] that is associated with a sense of complete evacuation. An SBM is a bowel movement that occurs in the absence of rescue medicine use or other laxative use (e.g. suppository or enema) on the calendar day of bowel movement or the calendar day before the bowel movement.

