#### 6.2. BASELINE AND STUDY DAY DEFINITIONS

Baseline definition will vary upon the data/variables for summaries/analyses.

Table 1: Baseline Definitions

Data/Variables	Baseline Definition
Laboratory, vital signs, and ECG	The last non-missing value prior to the first dose of the study drug
Breath CH 4 AUC measurement	AUC of breath CH 4 measurements collected during lactulose breath test performed at Screening after an overnight fast
Singe-point breath CH 4 measurement	A single-point breath CH 4 measurement collected at Randomization after an overnight fast
Weekly average score for worst abdominal pain in the past 24 hours	(Sum of daily pain scores) / (number of days with pain score assessment during the 7 days prior to the first dose of study drug)
Stool frequency of CSBMs per week/Weekly average number of CSBMs	7 x (sum of daily number of CSBMs) / (number of days with CSBM assessment

	during the 7 days prior to the first dose of study drug)
Stool frequency of SBMs per week/Weekly average number of SBMs	7 x (sum of daily number of SBMs) / (number of days with SBM assessment during the 7 days prior to the first dose of study drug.
Weekly average of bloating score	Sum of daily bloating scores / (number of days with bloating score assessments during 7 days prior to the first dose of study drug)
Weekly average of straining score	Sum of daily straining scores / (number of days with straining score assessments during 7 days prior to the first dose of study drug)
Adequate Relief	The last non-missing value prior to the first dose of the study drug
Weekly stool consistency score (BSFS)	Sum of (i $\times$ number of type i stools) / total number of stools during 7 days prior to the first dose of study drug, where stool consistency i = 1, 2,7
EQ-5D-5L score	The last non-missing value prior to the first dose of the study drug

Study day will be defined as follows:

- The first dose of study drug is designated as Day 1.
- For visit days after Day 1, study day = visit date Day 1 date + 1.
- For visit days prior to Day 1, study day = visit date Day 1 date. Thus, study days for screening visit are negative numbers. There is no "Day 0".

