#### **6.4.** MISSING DATA

For the analyses of various weekly responses, the week with missing assessments for more than 3 days will be treated as "non-responder" for the week. If a subject drops out of the study or otherwise does not report efficacy data for a particular treatment-period week, the subject will not be considered a responder for that week.

For the analyses of various weekly average scores for IBS symptoms, the weekly average score will be set to "missing" if there are more than 3 days with missing assessments during a week, and the data will be considered as "missing" for the week. An observed-cases approach to missing data will be applied to the continuous type variables; this means that if the data is considered as "missing" for the week, the average of the non-missing data over the 12 weeks of the treatment period will be the subject's value for that week.

Subjects will be assumed to have not had bowel movement nor taken rescue medication if the corresponding daily question is not answered.

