# 8.2. SECONDARY AND EXPLORATORY EFFICACY ENDPOINTS AND ANALYSIS

# 8.2.1. Secondary Efficacy Endpoints

The secondary efficacy endpoints are listed below:

- The proportion of overall responders during the 12-week Treatment Period (overall 12-week responders).
- Proportion of overall stool frequency responders during the 12-week Treatment Period.
- Proportion of overall abdominal pain intensity responders during the 12-week Treatment Period.
- Proportion of overall bloating responders during the 12-week Treatment Period.

• Proportion of patients using rescue medication.

The comparisons of the proportions will be performed using the Chi-squared test for equal proportions based on the full analysis set. The Chi-squared test from SAS Proc Freq will be used for the comparison of the treatment differences (each SYN-010 dose group versus placebo). Nominal P-values and 95% Newcombe-Wilson CIs for treatment differences will be presented.

To control the overall false positive rate, a fixed sequence testing procedure will be used for the testing of the secondary endpoints listed above. Specifically, the secondary endpoints will be tested formally if statistical significance is achieved for the primary endpoint for both dose groups, otherwise, the secondary endpoints will not be tested formally. If statistical significance is achieved for the primary endpoint for both dose groups, then the secondary endpoints will be tested formally in the order of the list for the 42 mg dose. The first listed secondary endpoint will be tested at the 2-sided alpha = 0.05 level. If statistical significance is not achieved, then the testing procedure will stop. If statistical significance is achieved for the first listed secondary endpoint, then the following secondary endpoint will be tested at the 2-sided alpha = 0.05 level. The testing procedure will continue for the testing of the secondary endpoints until statistical significance is not achieved for a secondary endpoint for the 42 mg dose group. If statistical significance is achieved for all listed secondary endpoints of the 42 mg dose group, then the testing procedure will be repeated for the 21 mg dose group.

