- Change from baseline in weekly stool consistency score (BSFS) at Weeks 1 through 12. Weekly stool consistency score = sum of (i × number of type i stools in a week) / total number of stools in the specific week, where i = 1, 2,...7.
- Proportions of overall abdominal pain intensity responders with different cutoff points for the % improvement from baseline in weekly average score for worst abdominal pain, i.e., ≥ 10%, 20%, 40%, 50%, 60%, and 70%.
- Proportions of overall stool frequency responders with different cutoff points for the improvements from baseline in the weekly number of CSBMs  $\geq 2, 3, 4, 5$ , and 6.

Proportions of overall bloating responders with different cutoff points for the % improvement from baseline in weekly average bloating score, i.e.  $\geq$  10%, 20%, 40%, 50%, 60%, and 70%.

The same analysis of covariance (ANCOVA) model will be used for the analysis of the continuous secondary endpoints. The model will include treatment group and the corresponding baseline value as covariates. Nominal P-values and least squares treatment means and their differences will be presented, accompanied by 95% CIs for each time point. The comparisons of the proportions will be performed using the Chi-squared test for equal proportions.

All analyses will be based on the full analysis set.

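### The weekly Bristol score counts stools that follow rescue laxatives, so unequal rescue use would shift this secondary endpoint towards softer stools in the heavier-rescue arm

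*SAP*

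**What the plan says.** **Stool consistency.** SAP Section 8.2.1 divides the type-weighted stool count by the "total number of stools in the specific week". SAP Table 1 (Section 6.2) uses the "total number of stools during 7 days prior to the first dose of study drug" for baseline. Neither is limited to spontaneous stools, and the endpoint lists in Protocol Sections 4.2 and 6.6 add no limit.

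**Stool frequency.** SAP Section 3.1 takes the opposite approach: "An SBM is a bowel movement that occurs in the absence of rescue medicine use or other laxative use". The window is the calendar day of the movement and the day before it.

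**Rescue.** Protocol Section 8.8: "Permitted rescue medications include bisacodyl, magnesium citrate, magnesium hydroxide, and lactulose". Apart from a short ban ("rescue medication will not be allowed the day before, the day of, or the calendar day after the Randomization Visit"), they may be used for severe constipation throughout. SAP Section 8.2.1 compares rescue use between arms: "Proportion of patients using rescue medication".

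**Data.** The daily questionnaire (Protocol Section 13.3) asks the stool form of each recorded movement and "Did you take a laxative today".

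**Analysis.** BSFS is analysed by ANCOVA on treatment and baseline BSFS, with nominal P-values. There is no rescue term and no rescue-related sensitivity analysis for BSFS.

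**Missing data.** SAP Section 6.4: "Subjects will be assumed to have not had bowel movement nor taken rescue medication if the corresponding daily question is not answered". The same section gives a continuous weekly value that is missing the patient's mean over the non-missing weeks of treatment.

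**The concern.** A stool produced by a laxative does not count as a spontaneous movement, yet its form counts towards the consistency score. Rescue is taken because constipation is bad, but a softened stool raises the Bristol mean, which in IBS-C reads as improvement. If one arm takes more rescue after randomization, its mean is raised by the laxative rather than by study drug. Adjusting for baseline BSFS cannot remove an imbalance that arises later. The consistency result could then disagree with the SBM and CSBM results only because the two are built on different sets of stools.

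**Working it through.** **The plan's own figure.** The documents give no design calculation for BSFS. Their only one is 90% power for CSBMs with 50 per arm, a difference of 1.0 and SD 1.5. It reproduces: SE = 1.5 × √(2/50) = 0.30, and power is 0.915 by the normal approximation and 0.910 by the noncentral t. This point does not dispute it.

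**One patient-week (assumed stools).** Three spontaneous type 2 stools score 2.0. Add two type 5 stools after a laxative and the score is (3×2 + 2×5)/5 = 3.2. That is a gain of 1.2 with no change in spontaneous stools.

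**Arm level.** Let m be the mean type of spontaneous stools, f the share of scored stools inside the laxative window, and s the amount by which those stools are softer. The all-stool mean is m + f·s. With a common s, the difference between arms A and B is

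(m_A − m_B) + (f_A − f_B)·s.

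The last term is the distortion. An SBM-only score removes it, apart from laxative use that goes unrecorded.

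**Inputs not in the documents.** f, s and the SD of BSFS are all assumed: gap in f of 0.05 to 0.20, s of 1 to 3 types, SD of 0.8 to 1.5. With 50 per arm, SE = SD × √(2/50) = 0.2 × SD. The table takes SD 1.0 (SE 0.20) and no true difference in spontaneous stool form. Each cell gives the distortion in Bristol points and the resulting two-sided rejection rate at a nominal 5% (normal approximation).

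| Gap in share | s = 1 | s = 2 | s = 3 |
|---|---|---|---|
| 0 | 0; 5% | 0; 5% | 0; 5% |
| 0.05 | 0.05; 6% | 0.10; 8% | 0.15; 12% |
| 0.10 | 0.10; 8% | 0.20; 17% | 0.30; 32% |
| 0.20 | 0.20; 17% | 0.40; 52% | 0.60; 85% |

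Over SD 0.8 to 1.5 and gaps of 0.05 to 0.20, the rate runs from about 5% to 96%. So wide a range shows how little the documents fix the size.

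**Baseline.** Baseline stools precede randomization, so laxative-affected stools are balanced between arms in expectation. The all-stool rule at baseline therefore does not itself bias the comparison.

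**The case against.** - **Choice of estimand.** Stool form regardless of rescue is a legitimate target, and an SBM-only score conditions on something that happens after randomization. This stands in part. But the SAP does not say that it intends that target, and it treats SBMs and CSBMs the other way. Reporting both scores meets the objection.
- **Little rests on BSFS.** The SAP's fixed sequence covers only the five proportions, and the futility rule in Protocol Section 6.6 uses CSBMs and overall responders. This stands and limits the weight of the point. Protocol Section 6.6 does order secondary tests by the list in Section 4.2, where BSFS comes last. The two documents should be reconciled on that.
- **Size and direction are assumed.** This stands.
- **An imbalance would be seen.** Rescue use is reported by arm, so a gross difference would be visible. But the proportion of patients who ever used rescue does not give the share of stools affected, and BSFS is not adjusted for it.
- **An SBM-only score brings its own bias.** If weeks without an SBM are set to missing, SAP Section 6.4 read plainly would fill them with the patient's mean over better weeks, more often in the heavier-rescue arm. This stands, so the fix must switch that rule off for these weeks.

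**Conclusion.** The point holds as a conditional one. Unequal rescue use after randomization shifts the weekly Bristol score towards softer stools in the arm that uses more, and nothing in either document corrects for it. Under the assumed ranges the shift is 0.05 to 0.60 points, and near zero if shares and shifts are equal. The primary endpoint is not affected.

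A reader might infer three stronger things that the documents do not support:

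1. *That placebo will use more rescue, so a true benefit is masked.* The planning assumption of a larger CSBM gain on active makes this plausible. But there are no rescue rates, and the guidance in Protocol Section 8.8 also needs high pain scores and leaves the decision to the investigator and patient. Heavier use on active would inflate the effect instead.
2. *That most of the effect would be lost, or its sign reversed.* Suppose spontaneous means of 3.0 and 2.2, and rescue stools of type 6 making up 10% of active and 20% of placebo stools. Then 3.30 − 2.96 = 0.34 instead of 0.80, a 58% loss. With rescue stools of type 4 it is 3.10 − 2.56 = 0.54, a 32% loss. Reversal in the type 6 case, with active at 10%, needs a placebo share above (3.30 − 2.2)/3.8 = 29%. Nothing in the documents supports any of these shares.
3. *That the baseline rule biases the arms.* It does not. It should change only so that baseline and treatment scores are built alike.

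**What to change.** In SAP Section 8.2.1 and Table 1, define the score as the sum of (i × number of type-i SBMs) divided by the total number of SBMs in the week, or in the seven baseline days. Keep the all-stool score as a sensitivity analysis.

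For BSFS, leave weeks with no SBM as missing. State that the replacement by the patient's 12-week mean in SAP Section 6.4 does not apply to them, and report their number by arm. Say also how a patient with no SBM in the baseline week is handled.

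The cost is a few lines of SAP text and one program filter. The diary already holds stool form and laxative use, and the primary endpoint already needs the SBM flag. The downside is more non-evaluable weeks, possibly unequal between arms. Some laxative-affected stools will also remain, because an unanswered laxative question counts as no rescue.

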## 8.2.2. Exploratory Efficacy Endpoints

Exploratory endpoints are listed as the following parameters:

- Proportion of subjects who have adequate relief of IBS symptoms.
- Change from baseline for SYN-010 in PROs using validated questionnaires in the REDCap system.
  - Change from baseline in weekly PAC-SYM scores, the averages of the PAC-SYM scores, abdominal, rectal, and stool symptom scores.
    - The average of the PAC-SYM scores is based on the 12 items from PAC-SYM, and is the sum of non-missing item scores within the instrument / the total number of non-missing items (score range, 0–4). The averages of the abdominal, rectal, and stool symptom scores are based on items 1-4, 5-7, and 8-12, respectively. Each average score is the sum of non-missing item scores within the subscale / the total number of non-missing items for that subscale (score range, 0–4).
  - O Change from baseline in weekly straining score at Weeks 1 through 12. Weekly average of straining score = (sum of daily straining scores / number of days with straining score assessment) for a specific week.
  - Assessment of Quality of Life measures using the EQ-5D-5L questionnaire.

- Change from baseline in the area-under-the-curve (AUC) of breath CH4 production, based on the 120-minute lactulose breath test.
- Change from baseline in breath CH4 production based on a single-point breath CH4 test.

The same analysis of covariance (ANCOVA) model will be used for the analysis of the continuous exploratory endpoints except for the serum cytokine levels.

For the EQ-5D-5L scores, the summary statistics will be provided for the 5 dimensions as stated in the 'EQ-5D-5L User Guide' by Mandy van Reenen and Bas Janssen. In addition, summary statistics will be provided for the EQ VAS scores and change from baseline in EQ VAS scores by treatment group.

# 8.2.3. Additional Exploratory Efficacy Endpoints

Additional exploratory efficacy endpoints will be evaluated as follows:

- Change from baseline in the area-under-the-curve (AUC) of breath H2 production, based on the 120-minute lactulose breath test.
- Comparison of serum cytokine levels at baseline and EOS measuring for potential immune or inflammatory signals to include the key cytokines of the Th1/Th2/Th17 pathways: IL-2, IL-4, IL-5, IL-9, IL-10, IL-13, IL-17, GM-CSF, and IFN-γ. Plus TNF-α, IL-12, IL-6, the two chemokines IL-8 and MCP-1, and the gut cytokine IL-25.
- Microbiome measurements in stool of bacteria (16S rRNA) and methanogens (qPCR).

The serum cytokine levels (IL-2, IL-4, IL-5, IL-9, IL-10, IL-13, IL-17, GM-CSF, IFN- $\gamma$ , TNF- $\alpha$ , IL-12, IL-6, IL-8, MCP-1, IL-25) and the microbiome measurements in stool of bacteria (16S rRNA) and methanogens (qPCR) will be summarized by treatment group with mean and standard deviation, median, and range at each time point. The nominal P-values from the Wilcoxon rank sum test for the change from baseline will be provided.

# 8.3. SUBGROUP ANALYSES

Subgroup analyses by race, gender, and BMI at Screening ( $<30, \ge30$ ) will be conducted for the following endpoints, using their corresponding statistical analysis method as mentioned before:

- Change from baseline in weekly average number of CSBMs at Weeks 1 through 12
- Proportion of overall responders during the 12-week Treatment Period
- Proportion of overall abdominal pain intensity responders during the 12-week Treatment Period.
- Proportion of overall stool frequency responders during the 12-week Treatment Period.
- Change from baseline in weekly average score for worst abdominal pain at Weeks 1 through 12.

- Percent change from Baseline in weekly average score for worst abdominal pain at Weeks 1 through 12.
- Change from baseline in weekly bloating score at Weeks 1 through 12

All the subgroup analyses will be based on the full analysis set.

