3.1 Background

Irritable bowel syndrome (IBS) is a gastrointestinal (GI) syndrome characterized by chronic abdominal pain and altered bowel habits in the absence of any organic cause. The symptoms of IBS not only adversely affect a patient's health-related quality of life (QoL), but also place a significant financial burden on society due to reduced work productivity and increased use of healthcare-related resources^{1,2}. Patients with IBS frequently complain of abdominal bloating and increased gas production in the form of flatulence or belching. The prevalence in North America and Europe is approximately $10-15\%^{3,4}$. Irritable bowel syndrome affects all ages and genders however there is a 2:1 female predominance in North America⁵. Irritable bowel syndrome is classified into 4 subtypes based on stool pattern: IBS with constipation (IBS-C), IBS with diarrhea, mixed IBS, and un-subtyped IBS. Irritable bowel syndrome with constipation is defined as the presence of hard or lumpy stools with \geq 25 percent of bowel movements and loose or watery stools with < 25% of bowel movements⁶.

SYN-010 is a modified release, oral formulation of lovastatin being developed for the treatment of IBS-C. The SYN-010 program is based predominantly on research by [name] (Director, Medically Associated Science and Technology Program, Cedars-Sinai Medical Center) and collaborators^{7,8,9} hypothesizing that reduction in intestinal methane (methane) production can reverse constipation and improve global symptoms in IBS-C. Methane production in humans is due to methanogenic archaea in the intestine, predominantly *Methanobrevibacter smithii* (*M. smithii*). Methane, the key product of anaerobic respiration of methanogens, had been perceived to produce no ill effects in humans aside from gaseous distention. However, several research groups worldwide have shown that a significant percentage of patients with IBS-C excrete methane, and elevated methane production by methanogens correlates with constipation and related symptoms in both IBS-C and chronic idiopathic constipation^{7,8,9,10,11,12,13}. A direct causative role for methane in IBS-C was demonstrated in a recent case report, wherein a woman undergoing fecal microbiota transplantation (FMT) for *C. difficile* infection unknowingly received stool containing a high concentration of methanogens. The FMT recipient rapidly developed severe symptoms of IBS-C that were subsequently reversed by ablation of methane production¹⁴.

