6.1 General considerations

A statistical analysis plan (SAP) describing all the statistical analyses to be completed will be finalized prior to database lock. Unless otherwise specified, for numeric data, descriptive statistics will include the number of patients with data to be summarized (n), mean, standard deviation (SD), median, minimum (min), and maximum (max). Categorical data will be presented using frequency counts and percentages. All statistical tests will be conducted at a 2-sided significance level of 5% unless otherwise specified.

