# 2.2. DETERMINATION OF SAMPLE SIZE

The sample size calculation is based on the following assumptions: the weekly CSBM change from baseline is 0.5 for the placebo group, and 1.5 for each active group, with common standard deviation of 1.5. Fifty subjects in each group will have 90% power for each SYN-010 group compared with the placebo by using the t-test with 2-sided alpha = 0.05.

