#### 8.1. PRIMARY EFFICACY ENDPOINT AND ANALYSIS

The primary endpoint is the change from baseline in the weekly average number of CSBMs during the 12-week treatment period.

The analysis for the primary endpoint will be performed using the analysis of covariance (ANCOVA) with treatment group and the baseline value as covariates based on the full analysis set. The primary analysis will be conducted using the observed values. To control the overall false positive rate at 0.05, the Hochberg testing procedure will be used. Specifically, let  $P_1$  and  $P_2$  be the P-values from the ANCOVA comparing the 42 and 21 mg dose group with the placebo, respectively, if  $Max(P_1,P_2) \leq 0.05$ , then the primary endpoint will achieve statistical significant for both doses. Otherwise, if  $Min(P_1,P_2) \leq 0.025$ , then the primary endpoint will achieve statistical significance for the dose that has smaller P-value. If  $Min(P_1,P_2) > 0.025$ , then the primary endpoint will not achieve statistical significance for either dose group. The nominal P-values and 95% confidence intervals (CI) will be provided from the ANCOVA model.

Two sensitivity analyses will be conducted by using the multiple imputation and last observation carried forward (LOCF) methods to impute the missing data for the primary endpoint. The same ANCOVA model will be used for the sensitivity analyses.

In addition, the analyses of the primary endpoint will be performed based on the PP population using the same statistical model.

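### SAP 8.3 repeats the main tests within each sex, BMI and race group without an interaction test, so it does not test whether the effect differs between groups

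*SAP*

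**What the plan says.** SAP 8.3 plans "Subgroup analyses by race, gender, and BMI at Screening", with BMI cut at 30, for seven endpoints. Four are continuous and listed for Weeks 1 through 12: change in CSBMs, change and percent change in worst abdominal pain, and change in bloating. Three are 12-week responder proportions: overall, abdominal pain intensity and stool frequency. The method is given only as "using their corresponding statistical analysis method as mentioned before".

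Tracing that back:

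- SAP 8.1 and 8.2.1 use ANCOVA with treatment group and baseline for continuous endpoints. For the primary endpoint, "The nominal P-values and 95% confidence intervals (CI) will be provided from the ANCOVA model". For the continuous secondary endpoints, SAP 8.2.1 asks for P-values, least squares differences and intervals at every time point.
- SAP 8.2.1 uses the Chi-squared test, each dose against placebo, for proportions, with nominal P-values and Newcombe-Wilson intervals.
- Protocol 6.1 adds: "All statistical tests will be conducted at a 2-sided significance level of 5% unless otherwise specified".

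Neither document mentions a treatment-by-subgroup interaction, a rule for reading subgroup results, a minimum subgroup size, or how race will be grouped. SAP 8.3 does not call the analyses exploratory or descriptive. By contrast, SAP 9 rules out inferential statistics for safety.

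**The concern.** Neither main method contains a subgroup term, so the natural reading of SAP 8.3 is that each test is rerun inside each level of each factor. A subgroup analysis should ask whether the treatment effect differs between levels, and separate tests do not answer that. Whether each reaches 5% depends heavily on how many patients are in the level. When the effect is the same everywhere, the larger group will often be significant and the smaller one not.

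A reader given P-values by sex, BMI class and race may conclude that the drug works in one group and not in another. In a Phase II trial that is a costly misreading, although the documents do not say what subgroup results will be used for.

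**Working it through.** **Inputs.** From SAP 2.2: "the weekly CSBM change from baseline is 0.5 for the placebo group, and 1.5 for each active group", a difference of 1.0, "with common standard deviation of 1.5", 50 per arm, two-sided alpha 0.05, t-test. The documents give no enrolment split by sex. Protocol 3.1 says of IBS in North America that "there is a 2:1 female predominance". I use 2:1 as an assumption, 33 women and 17 men per arm, and vary it.

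**The plan's own figure.** The standardised difference is 1.0 / (1.5 × √(2/50)) = 1.0 / 0.30 = 3.33. Power is Φ(3.33 − 1.96) = 91.5% by the normal approximation and 91.0% by noncentral t. The stated 90% is reproduced.

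**Power within each sex, same true difference of 1.0.**

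- Women: SE = 1.5 × √(2/33) = 0.369. Power is 77.3% (normal) or 76.0% (exact t).
- Men: SE = 1.5 × √(2/17) = 0.514. Power is 49.3% (normal) or 47.0% (exact t).

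**Split result.** Men and women are different patients, so the two tests are independent:

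P(split) = p_w(1 − p_m) + p_m(1 − p_w)

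With the exact t powers, women only is 0.760 × 0.530 = 40.3% and men only is 0.240 × 0.470 = 11.3%. The total is 51.5% from unrounded powers. Both sexes are significant in 35.8% and neither in 12.7%. The normal approximation gives 50.4%. A simulation of about 12,000 trials with a random 2:1 split gives 52.4% for one dose, and 73% for at least one of the two doses. In the same simulation an interaction test is falsely positive in 5.0%.

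**Sensitivity (exact t, one dose; 33/17 unless stated).**

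| Varied | Split result |
|---|---|
| Women 50%, 60%, 70%, 75%, 80% | 46.3%, 48.3%, 54.4%, 59.8%, 64.0% |
| Baseline correlation 0.3, 0.5, 0.7 (residual SD 1.43, 1.30, 1.07) | 49.6%, 43.7%, 26.8% |
| True difference 0, 0.5, 0.75, 1.25 | 9.5%, 33.9%, 50.7%, 37.2% |
| 7.5% loss (4 of 53, Protocol 6.6) | 53.1% |
| Only the 53 patients randomized so far, 2:1 split | 39.7% |

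**Number of tests.** Four weekly endpoints × 12 weeks + 3 responder endpoints = 51 per dose and level. With 2 doses and at least 6 levels (two each for sex and BMI, at least two for race), 51 × 2 × 6 = 612 P-values. If the drug had no effect at all, about 612 × 0.05 = 31 would fall below 0.05. That is a different scenario from the 51.5%, which assumes the full design effect; with no effect the split rate is 2 × 0.05 × 0.95 = 9.5%.

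**Power of an interaction test.** At 33/17, the SE of the difference between the two sex-specific effects is √(0.369² + 0.514²) = 0.63. If the effect were 1.0 in one sex and zero in the other, power would be Φ(1.0/0.63 − 1.96), about 35%.

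**The case against.** The strongest reply is that the plan issues no subgroup verdicts. Formal testing in SAP 8.1 and 8.2.1 covers the primary endpoint and five listed secondary endpoints in the whole full analysis set. The other P-values are called nominal, and SAP 8.3 sets no success rule. This stands: the trial's type I error is untouched, and the harm arises only if someone reads the tables as a comparison between groups.

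Confidence intervals for treatment differences already come with the main methods, so part of the remedy is planned. That also stands. What is missing is the interaction and the exploratory label.

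The size of the effect is uncertain. The 2:1 ratio is background prevalence for IBS in general, not a forecast for methane-positive IBS-C patients at one centre. The sizing assumptions are not week-specific, whereas SAP 8.3 lists weekly endpoints, and the documents give no effect or SD by week. The split falls well below half with strong baseline adjustment or a smaller true effect. All of this stands and is why a range is shown. Even so, 27% is about five times the interaction test's error rate.

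Some stronger readings are tempting but unsupported. A reader might infer opposite effects in men and women: significant effects in opposite directions occurred in under 0.01% of simulated trials. A reader might infer that unequal group sizes create false effect differences: size changes precision and P-values but does not bias the estimates. A reader might carry the 51.5% over to BMI, race or the responder endpoints: the documents give neither the shares nor the responder rates needed.

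**Conclusion.** The point holds as a flaw of method and interpretation. As written, SAP 8.3 does not test whether the treatment effect differs by sex, BMI or race, and its within-group P-values invite that inference. With an identical effect in both sexes at the design values, one sex is significant and the other is not in 51.5% of trials, for one dose on CSBMs, against 5% false positives for an interaction test. This rests on a difference of 1.0, SD 1.5, 50 per arm and an assumed 2:1 female split. The figure is 46% to 64% for 50% to 80% women, 27% to 50% for a baseline correlation of 0.7 to 0.3, and 34% at a true difference of 0.5. No figure can be given for BMI, race or the responder endpoints. The change is worth making before database lock, but it does not bear on the validity of the primary analysis.

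**What to change.** Rewrite SAP 8.3 as follows.

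1. For each factor, fit one model to the full analysis set with treatment, baseline, subgroup and treatment-by-subgroup interaction; use logistic regression for the responder endpoints.
2. Report the treatment difference in each subgroup with its 95% confidence interval, and the interaction estimate with its interval and P-value. Drop within-subgroup P-values.
3. Use the 12-week average in place of 12 weekly tests for all four weekly endpoints.
4. Define the race groups in advance. Protocol Appendix 13.6 lists five categories and allows more than one to be chosen.
5. State that the subgroup analyses are exploratory.

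The cost is SAP wording, with fewer tables than now planned. The gain is limited: power is about 35% even if the effect is 1.0 in one sex and zero in the other, so a non-significant interaction would not show that the effects are equal. Some multiplicity also remains. Seven endpoints × 3 factors × 2 doses is 42 interaction contrasts if race has two groups (more otherwise), with about 42 × 0.05 = 2 false positives expected if no interaction exists. The exploratory label should say that these are not adjusted.
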